OFFICIAL TITLE: Study of Dilute Veregen ®, 10% sin catechins ointment, a botanical FDA approved drug derived from Green Tea Leaves Camellia sinensis, for the Treatment of Significant to Severe Vulvar Pain from Secondary Provoked Vestibulodynia in Sexually Active, Post-Menopausal Women with Vulvovaginal Atrophy

DOCUMENT DATE: MAY 13, 2020

NCT: 03682601

Protocol Amendment: Dated May 13, 2020

[name]., F.A.A.D.

GTO Pharmaceutical, LLC

Protocol Title: Study of Dilute Veregen ®, 10% sin catechins ointment, a botanical FDA approved drug derived from Green Tea Leaves Camellia sinensis, for the Treatment of Significant to Severe Vulvar Pain from Secondary Provoked Vestibulodynia in Sexually Active, Post-Menopausal Women with Vulvovaginal Atrophy

Rationale for Request for Amendment:

The study of postmenopausal women not taking estrogens has shown that the vaginal maturation index did not change with the topical dilute Veregen® ointment. This was an expected outcome. Veregen ®, or 15% sin catechins ointment derived from green tea is a known antiproliferative, anticancer drug evidenced in the medical literature. The lack of change in the vaginal maturation index will continue to enable postmenopausal women who chose not to or can not use estrogens to use a topical botanical drug made

from green tea to help alleviate provoked vestibular pain. They will continue to be enrolled in the trial.

It is now our mission to also enable postmenopausal women who are already using an estrogen to maintain the beneficial effects of their estrogen treatments on their vaginal epithelium but who may still be experiencing provoked vulvar vestibular pain to have access to a topical drug to address their vulvar vestibular pain.

The requested change in the protocol is the elimination of the exclusion criteria of estrogen (or an estrogen prodrug usage):

1. Have taken estrogen-containing treatments, either by systemic or local route, for three months or more.
2. Have used estrogen, including vaginal conjugated equine estrogen, or estrogen progestin therapy, vaginal oestrinol or low-dose vaginal oestradiol or any other exogenous estrogenic compound pharmaceutical including OTC plant based estrogenic substances in the last 12 weeks. Have used tablet or powder forms of phyto-estrogens for less than 12 weeks prior to Visit 1 (Week 0).
3. Have occasionally used (averaging more than once a week) in the past 30 days the following preparations that may interfere with the study purpose: DHEA or other drugs or supplements that may, in the opinion of the Investigator, affect sexual function.

PROTOCOL: Study of Dilute Veregen ®, 10% sinecatechins ointment, a botanical FDA approved drug derived from Green Tea Leaves Camellia sinensis, for the Treatment of Significant to Severe Vulvar Pain from Secondary Provoked Vestibulodynia in Sexually Active, Post-Menopausal Women with Vulvovaginal Atrophy

1. STUDY SYNOPSIS:

Introduction:

Secondary provoked vestibulodynia is defined as significant to severe pain of at least 3 months durations, in the vulvar vestibule during normal manipulation of the vulvar vestibule that is significant enough to cause the afflicted woman distress. Secondary vs primary provoked vestibulodynia is distinguished by whether the pain has been present since the patient's first episode of vaginal penetration (ie, lifelong or primary provoked vestibulodynia (PPVD) or after a period of pain-free activities (ie acquired or secondary provoked vestibulodynia (SPVD). This study is for women with secondary provoked vestibulodynia where a woman recalls a previous time when she did not experience vestibulodynia. Provoked indicates that a stimulus is needed to invoke the pain. For example, intercourse, masturbation, a tampon, digital manipulation or any other provocation. Pain at rest without manipulation is considered "unprovoked" and not the subject of this study.

One cause of secondary provoked vestibulodynia may be the use of exogenous progesterone(s) leading to the aberrant proliferation of nociceptive (pain) sensory fibers in the vulvar vestibule. Topical estrogen creams are among the many different inconsistent or non-efficacious treatments for SPVD in post-menopausal women. Leclair CM¹, Goetsch MF, Li H, Morgan TK. Histopathologic characteristics of menopausal vestibulodynia Obstet Gynecol. 2013 Oct;122(4):787-93. Not all menopausal women wish to take estrogen and for some women this type of treatment is medically contraindicated.

The study drug is Veregen® (sinecatechins) Ointment, an FDA approved, 2006, marketed botanical drug product for topical use in the treatment of external genital warts. The drug Veregen® is 15% sinecatechins, which is a partially purified fraction of the water-soluble extract of green tea leaves from Camellia sinensis, and is a mixture of catechins and other green tea components. Veregen ® is indicated to be topically applied as multiple 0.5 cm strands (i.e., to each and every visible genital wart) three times a day, continuously, for up to 16 weeks. In contrast, the study will be using Veregen ® ointment diluted, by the certified compounding pharmacy, with USP petrolatum w/w, to a drug concentration of 10% sinecatechins.

This diluted Veregen, 10% sinecatechins ointment, will be topically applied to the external genitalia, (vulvar vestibule) as a single ½ inch strand, once a day, for 4 weeks.

The rationale for using 10% Veregen once daily as a single ½ inch strand for a total of 4 weeks vs 6 weeks is that it was demonstrated in private practice to be both therapeutically efficacious during this time interval and without irritation.

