5. Have evidence of clinically significant organic disorder on the history and/or physical examination that would, in the opinion of the Investigator, put the patient at risk, prevent the patient from completing the study, or otherwise affect the outcome of the study.
6. Have a history of genital herpes because of the episodic nature of genital herpes and of the known possibility of occurrence of herpetic pain without visible dermatologic manifestations of herpes. Genital herpes and its accompanying genital pain may obscure the source of the genital pain experienced and confound the ability to determine the efficacy of treatment/placebo on endpoint of alleviation of pain in women with SPVD.
7. Have any infection of the genitalia
8. Have lichen sclerosis, lichen planus, contact dermatitis, psoriasis or any inflammatory condition or abrasions of the vulva
9. Have an episiotomy scar in the area where pain is perceived as it may confound the etiology of the perceived pain
10. Have diabetes.

5. STUDY PROCEDURES:

Duration of Study:

Once subjects are screened and enrolled into the study, the duration of participation in the study will be 4 weeks from the beginning of the study to the last visit. Follow up questionnaires will be filled out at 6 weeks and electronically entered or mailed in to your clinical trial gynecologist's study clinic office.

Subjects will be given a written description of the study and possible untoward effects of the protocol. They will sign the IRB-approved informed consent. The schedule and activities of visits will be given to the subject, along with instructions about notification in case of untoward events.

Accepted subjects will be randomized and only a non-participant in the clinical trial will hold the code. Except for subjects who decide to leave the trial because of any adverse reactions (i.e.. irritation), prior to its completion, the code will not be broken prior to the completion of the last subject's protocol.

Study Procedures:

Each and every procedure performed is a standard procedure. These procedures will be performed at a screening visit and each of the three subsequent study clinic visits. Initial screening; week 0, week 2; week 4 . Please note, in addition to study related procedures that a standard of care medical history, including past and current medical history, medications, allergies, height, weight and blood pressure will be taken initially and reviewed for any changes on each study clinic visit.

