The schedule and activities of visits will be given to the subject, along with instructions about notification in case of untoward events.

WEEK	0 1	2	3	4	6			3 4 5	6	12	
Pain level (NRS), SAL	X X	X	X	X	X				diary	Mail-in	
History, Exam, MI, pH, Q-tip	X	X		X				—	x		
FSFI, VVSQ, FSD-R	X	X		X	X			x	x	Mail-in	

Patients will be enrolled in the study and randomized to treatment only after all the inclusion and exclusion criteria have been satisfied.

(Visit 1) Week 0

Patients will come to the study clinic to be screened according to the protocol inclusion/exclusion criteria at their first visit prior to randomization into the study. Site personnel must register the patient with the interactive voice response system (IVRS) at this visit to obtain a patient number.

After patients have signed the informed consent, site personnel will review the inclusion and exclusion criteria to ensure that the patient is eligible for the study. The following information will be recorded, or procedures performed for eligible patients. Verbal questioning is to be completed before any invasive procedures are undertaken.

1. Personal and demographic information.
2. Medical/gynecological history including year of last menstrual period to establish post-menopausal state.
3. Drug history (prescription/non-prescription/herbal supplements, including DHEA) for the previous 3 months.
4. Physical examination: The intake pelvic examination, including of the vulva and vagina, will be normal for a woman's age and years since menopause.
5. Vaginal Maturation Index
6. Vaginal pH, bacterial screening swab
7. Q-tip Test to establish localization and rating NRS of vulvar, vestibular pain.
8. Vital signs including blood pressure and heart rate (after sitting 5 minutes) and body temperature, height and weight.
9. Assessment of acute life stress relating to any major life change that interferes with sexual function.
10. Status of patient's sexually functional, both psychologically and physically
11. Establishing that patient is sexually active with self (masturbation) and/ or with partner.
12. During the consent process, all of the questionnaires (including SAL, FSFI, NRS, VVSQ, FSDQ-R) will be reviewed with the patients to allow them to read what they will be expected to complete during their participation in the pre-treatment, treatment and post-treatment periods of the study.

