The study medication and placebo have a red brown color and may therefore stain underwear. Subjects will be advised to wear panty liners every day that they apply the study medication in order to avoid staining of their underwear with the medication or placebo.

7. Monitoring and Reporting of Adverse Events/Serious Adverse Events: During the study, if you experience any medical problems, suffer a research-related injury, or have questions, concerns or complaints about the study, please contact your clinical trial gynecologist. If you seek emergency care, or hospitalization is required, alert the treating physician that you are participating in a research study being conducted by your clinical trial gynecologist.

Monitoring of Adverse Events will be done by patients reporting any adverse event to their clinical trial gynecologist. No serious adverse events are expected.

8. Study Oversight: In the unlikely event of the need to prematurely terminate this study of 10% , [name] will be the one to decide to terminate the study. The study will be made available for monitoring, auditing, IRB review and regulatory inspection by providing direct access to study related source data.

9. Data Management- Preliminary Power Analyses and Sample Size Estimates

Power Analyses

For Primary Outcome: Pain Score:

Sample size was calculated to achieve at least 80% power with a significance level of 0.05 using a two-tailed, two-sample t test. A sample size of 56 subjects (28 subjects in treatment group and 28 subjects in the placebo group) was estimated to achieve 80% power to detect at least 2.0-points mean difference between treatment and placebo groups. The Initiative on Methods, Measurement, and Pain Assessment in Clinical Trials suggests that reductions in pain intensity of at least 15–20%, or 2 points in the 0–10 scale, reflect clinically important changes (Dvorkin et al, Core Outcome Measures for Chronic Pain Clinical Trials:

IMMPACT Recommendations Pain: 2005 Jan; 113 (1-2) pp: 9-19)). The pain classification on a 0-10 scale will be as follows: 0 no pain; 1-3 mild pain; 4-6 moderate pain; 7-9 significant pain; 10 severe pain. To compensate for possible withdrawal of 15% of patients in the vulvodynia study, a total sample size of 64 participants (32 in the treatment group, 32 in the placebo group) will be required.

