12. Intended Use of the Data: Should the study confirm the efficacy of 10% sinocatechins ointment (diluted Veregen®) in relieving or curing secondary provoked vestibulodynia in post-menopausal women without any significant effect on the maturation of the vaginal epithelium an excellent option will be available for women who suffer with this life altering condition. It would be a therapeutic option for postmenopausal women especially who because of a past history of gynecologic malignancy would be unwilling or unable to use estrogens A paper may be formulated and presented for publication in the medical literature.

The data is intended to test and therefore confirm the efficacy of local 10% sinocatechins ointment (Green Tea ointment) in the reduction or elimination of secondary provoked vestibulodynia with the added benefits of increasing lubrication and improving sexual function without demonstrable effects on the vaginal epithelium.

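### Estrogen users are admitted mid-trial, but the plan has no stratification factor, covariate or pre-specified estimate by estrogen use

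*Combined protocol and SAP*

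**What the plan says.** The Rationale for Request for Amendment keeps women who do not use estrogen in the trial and adds a second group: "It is now our mission to also enable postmenopausal women who are already using an estrogen". The only change it requests is removal of three estrogen-related exclusion items, one of which covered estrogen-progestin therapy.

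On allocation, section 5 (Duration of Study, and again under Consent Protocol) says "Accepted subjects will be randomized and only a non-participant in the clinical trial will hold the code". No stratification factor is named. An IVRS is in use from Visit 1.

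On size, section 9 says "Sample size was calculated to achieve at least 80% power with a significance level of 0.05 using a two-tailed, two-sample t test", with 28 evaluable women per arm "to detect at least 2.0-points mean difference between treatment and placebo groups", raised to 64 in total for withdrawal. The Statistical Analyses text lists chi-square, t test, ANOVA and Mann-Whitney. It contains no term, subgroup or interaction for estrogen use.

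The information needed is already collected. Visit 1 records "Drug history (prescription/non-prescription/herbal supplements, including DHEA) for the previous 3 months".

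Three parts of the text still describe non-estrogenized women only: the objective in section 3, inclusion criterion 3 in section 4, and item 15 of Visit 1. Section 12 directs the result especially to women who "would be unwilling or unable to use estrogens".

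**The concern.** After the amendment one comparison serves two groups. The rationale is interested in users and section 12 in women who cannot or will not take estrogen, yet no estimate is planned for either.

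The plan itself gives reasons to treat hormone use as a relevant baseline factor:

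- Estrogen use was an exclusion until this amendment.
- The Introduction names exogenous progesterone as a possible cause of the condition, and some users may now be taking combined therapy.
- The objective asks for pain relief without an estrogenic effect on the vaginal epithelium, and a user's own estrogen acts on that same measure.

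If nothing is written down before unblinding, any later split by estrogen use will be post hoc. An uneven share of users between arms would then have no planned adjustment, and a pooled result could be read as evidence for users on very few women.

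**Working it through.** **Inputs.** From section 9: two-sided 0.05, 80% power, difference 2.0 points, 28 evaluable per arm, 32 per arm randomised. Not in the documents, and so assumed: the number of users (10 to 32 of 64, a share of 16-50%) and the difference in pain between users and non-users (1 to 2 points).

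**1. The plan's own figure.** No SD is stated, so the 56 cannot be reproduced independently. Solving backwards with the noncentral t, 28 per arm gives 80% power at a standardised difference of 0.7624. The implied SD is 2.0 / 0.7624 = 2.62. The standard error of the arm difference is 2.62 × √(2/28) = 0.70.

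**2. Precision gained by adjustment.** If a share f of women are users and they differ by D points, the residual variance is 2.62² − D² × f(1−f), with 2.62² = 6.88 from the unrounded SD. The one degree of freedom spent on the factor is ignored.

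| D | f | Residual variance | Residual SD | Power, 28 per arm |
|---|---|---|---|---|
| 1 | 0.16 | 6.88 − 0.13 = 6.75 | 2.60 | 81% |
| 1 | 0.50 | 6.88 − 0.25 = 6.63 | 2.58 | 81% |
| 2 | 0.16 | 6.88 − 0.53 = 6.35 | 2.52 | 83% |
| 2 | 0.50 | 6.88 − 1.00 = 5.88 | 2.43 | 86% |

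**3. Chance imbalance.** A gap of 15 percentage points is 0.15 × 32 = 4.8 women. With an even number of users, that means a gap of at least 6. The hypergeometric chance depends on how many women were still to be randomised at the amendment, which is not stated. The last two columns assume that earlier allocation was balanced.

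| Users | Spread over all 64 | 48 remaining | 32 remaining |
|---|---|---|---|
| 10 | 8% | 7% | 5% |
| 20 | 18% | 14% | 7% |
| 32 | 21% | 12% | 0% |

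Users were excluded before the amendment, so the first column is an upper value. A 6-woman gap shifts the unadjusted difference by 6/32 × (1 to 2) = 0.19 to 0.38 points. Against the standard error of 0.70, that is about a quarter to a half of one standard error.

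**4. What could be said within each group.** For m users per arm, with no withdrawals, the 95% CI half-width is t(0.975, 2m−2) × 2.62 × √(2/m).

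| m | Half-width | Power for 2.0 points |
|---|---|---|
| 5 | 2.306 × 2.62 × √(2/5) = 3.8 | 19% |
| 10 | 2.101 × 2.62 × √(2/10) = 2.5 | 36% |
| 16 | 2.042 × 2.62 × √(2/16) = 1.9 | 55% |

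For non-users among the 56 evaluable women, power is 76%, 67% or 49% when users make up 10%, 25% or 50%. At an even split (14 per arm in each group), an assumed SD of 2.0 gives 72% and an SD of 3.0 gives 40%.

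**5. Maturation index and pH.** No arithmetic applies. In a non-user, the protocol offers no other estrogen source for a change in these measures. In a user, her own treatment is a second source. Criterion 3 limits the problem, because every entrant must be atrophic at screening, but it does not remove it.

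**The case against.** The strongest reply is that nothing here is biased. A reader might infer that, with the two groups pooled, neither population's result can be read from the trial. The documents do not support that. Randomisation keeps the pooled comparison valid for the mixture enrolled, and the drug history allows an estimate in either group. What is missing is pre-specification and precision.

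A reader might also call the 0.19-0.38 point shift a bias. It is chance variation already inside the standard error of 0.70, and it rests on an assumed 1-2 point difference with no source in the documents. The Introduction calls topical estrogen creams inconsistent or non-efficacious for this pain, which argues against a large difference. Its remark on progesterone applies only to users who also take a progestogen, and their number is unknown.

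A third inference is that users will respond less and sink the overall test. If users gained nothing and non-users 2.0 points, pooled power would be 56% with 25% users and 29% with 50%. The documents give no evidence of such a difference in response.

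Two further points stand. The retained atrophy criterion may let in few users, so the upper end of the assumed range is speculative, and it weakens the argument that users cloud the maturation index result. The main objective was also never rewritten as a separate claim in users, and low power in a subgroup is usual at this size. Stratification adds little beyond adjustment at this N. None of this removes the value of writing the adjustment and the separate estimates down in advance.

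**Conclusion.** The concern holds as a gap in pre-specification and efficiency; it does not invalidate the trial. The amendment changes who may enter, and the plan says nothing about how estrogen use is handled in allocation or analysis, although it is recorded. The expected gain in power from adjustment is modest, 1 to 6 percentage points. The larger loss is interpretive: no statement for users or non-users is planned, and within users power for the plan's own 2.0-point difference would be 55% at best over the range considered.

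These figures rest on the implied SD of 2.62, an assumed 10 to 32 users, and an assumed 1-2 point difference in pain. That the amendment changed only the exclusions rests on its own account of the change.

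Separately, the aim of reaching women whose epithelium is maintained by estrogen does not agree with the retained objective (section 3), inclusion criterion 3 (section 4) and Visit 1 item 15 (section 5). These passages must be reconciled.

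**What to change.** Before unblinding:

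1. Include estrogen use at entry (yes/no, from the Visit 1 drug history) as a factor in the pain analysis. Where the IVRS allows, stratify the remaining randomisations by it.
2. Report the pain difference with its 95% CI separately for users and non-users, labelled exploratory, and state that the trial is not sized for a claim in users.
3. Base the conclusion of no estrogenic effect on maturation index and pH on non-users, with all women as supportive.
4. Reconcile the amendment's stated aim with the retained objective and atrophy criterion, so that it is clear which users the pooled population contains.

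The cost is SAP wording and, if used, one IVRS setting. No new data or additional women are needed. The downside is that the statement about users becomes explicitly exploratory, and the maturation index and pH conclusion rests on fewer women.

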64 women will be recruited from the practices of gynecologists and their colleagues. Inclusion criteria will include being sexually active (either with partner or self), post-menopausal, (without spontaneous menses for at least one year, a non-estrogenized vaginal maturation index and a vaginal pH >4.6); experiencing at least 3 months duration with, at least, significant pain on the Numerical Rating Scale (NRS) 0-10-point scale (0-no pain, 1-3 mild, 4-6-moderate, 7-9-significant, 10-severe pain) from secondary provoked vestibulodynia (SPVD). The pain must be significant enough to cause them distress as measured by Female Sexual Distress Scale-Revised (FSDS-R). A score of ≥ 11 effectively discriminates between women with Female Sexual Distress and no FSD. The pain must be significant enough to affect their sexual function, Female Sexual Function Index (FSFI) with a score of 26 or less and effect their sexual activities noted weekly with the standard Sexual Activities Log (SAL).

The intake pelvic examination, including of the vagina, will be normal for a woman's age and years since menopause.

Subjects may or may not have points of erythema in the vulvar vestibule as is common in women suffering from provoked secondary vestibulodynia.

A subject to be included in the study, must have at least significant (7) or above on the Numeric Rating Scale (NRS) of pain intensity (NRS) during the Q-tip test performed at the initial screening visit. Whereas, the Q-tip test must elicit at least significant pain intensity, visible erythema is not necessary to be included in the study. The descriptive characteristics of the pain will be documented using the standard Vulvovaginal Symptoms Questionnaire (VVSQ).

Inclusion Criteria:

Generally healthy women must meet the following eligibility criteria:

1. For surgically menopausal women, be 20-70 years of age and at least 12 months post menopause.
2. For naturally postmenopausal women, be 40-70 years of age and at least 1 year post menopause (defined as no spontaneous menses for 1 year).
3. In screening their vaginal pH will be 4.6 or greater and their vaginal maturation index will be consistent with vaginal atrophy. Vaginal atrophy is thinning, drying and of the vaginal walls due to having less estrogen in the body.

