4. Be, sexually functional, both psychologically and physically, whereby a woman is to be psychologically interested in sexual activity and physically sexually active with regular vestibular including vaginal introital genital manipulation whether through masturbation or partner sex, whether using digits, oral sexual contact, sex toys, and/or penile penetration present at regular intervals each month during the 4-week pre-treatment and the 4 - week treatment period of the study and the 6 th- week follow-up period of the study.
5. Be able and willing to participate in the study as evidenced by providing written informed consent.
6. Answer affirmatively to ALL of the following questions:
 - a. Before your vulvar pain, would you say that in general, your sex life was good and satisfying?
 - b. Since you have been experiencing vulvar pain, do you feel you have experienced a meaningful loss in your desire for sex?
 - c. Since experiencing vulvar pain, do you feel you have experienced a significant decrease in your sexual activity?
 - d. Are you concerned or bothered by your current level of arousal, desire for or interest in sex?
 - e. Would you like to see an increase in your level of interest, arousal or desire for sex and sexual activity?

Exclusion Criteria:

Women will be screened for study participation according to the following exclusion criteria at Visit 1 (Week -4) or as specified. Eligible women must not:

1. Have any physical limitations or sexual trauma that would interfere with normal sexual function.
2. Have used within the last 12 weeks any of the following medications/preparations that may interfere with the study purpose: systemic corticosteroids (acute use for fewer than 7 days is accepted), SSRI's, tricyclic antidepressants, anti-androgens, spironolactone, PDE5 inhibitors (Viagra®),
3. Be experiencing any chronic or acute life stress relating to any major life change, such as recent loss of income or the death of a close family member, that may, in the opinion of the Investigator, significantly interfere with sexual function.
4. Have significant psychiatric disorder, a significant alcohol or drug dependency and/or be receiving pharmacologic treatment for such illness or disorder.

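### The amendment admits hormone users with no stable-use rule and no use of hormone status in randomisation or analysis, which adds noise and leaves the no-estrogenic-effect conclusion unreadable in those women

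*Combined protocol and SAP*

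**What the plan says.** The Rationale for Request for Amendment describes its change as follows: "The requested change in the protocol is the elimination of the exclusion criteria of estrogen (or an estrogen prodrug usage"). Three items are then listed for removal:

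- Item 1: estrogen-containing treatment for three months or more.
- Item 2: estrogen, estrogen-progestin or plant-based estrogen in the last 12 weeks.
- Item 3: recent use of "DHEA or other drugs or supplements that may, in the opinion of the Investigator, affect sexual function".

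The stated purpose is to admit women who already use estrogen, keep its epithelial benefit and still have provoked pain.

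The current exclusion list in Section 4 has no estrogen, progestin, phyto-estrogen or DHEA item. Exclusion Criterion 2 remains for other drugs. It opens "Have used within the last 12 weeks any of the following medications/preparations that may interfere with the study purpose" and names, among others, systemic corticosteroids, anti-androgens and spironolactone.

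Inclusion Criterion 3 is unchanged: pH must be 4.6 or greater, and "their vaginal maturation index will be consistent with vaginal atrophy". Section 5 (Visit 1, item 15) again asks for a non-estrogenised pH.

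A three-month drug history is taken at Visit 1 and updated at weeks 2 and 4, and the week 6 mailing asks about medication changes. Section 9 (Statistical Analyses) has no stratum, covariate or subgroup for hormone use, and names no test for the maturation index or pH.

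**The concern.** The objective in Section 3 has two parts: pain relief beyond placebo, and no estrogenic effect on the vaginal epithelium. The second part is read from the maturation index and pH, the measurements that exogenous estrogen is expected to move.

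The amendment intends women already established on estrogen, but no criterion says so. A woman who began a hormone shortly before Visit 1 is eligible if her epithelium still looks atrophic. If her index then rises, the plan cannot separate the hormone from the ointment.

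Pain could also be affected. The Introduction states: "One cause of secondary provoked vestibulodynia may be the use of exogenous progesterone(s) leading to the aberrant proliferation of nociceptive (pain) sensory fibers". Use of estrogen-progestin is now unrestricted.

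The other-drugs clause of item 3 was removed without a reason, although sexual function is measured by the FSFI and the Sexual Activities Log.

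**Working it through.** **1. What each rule admits.**

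| User of estrogen at screening | Amendment | Criterion 3 |
|---|---|---|
| Stable, epithelium responding | meant to be added | screened out |
| Recent starter, no response yet | not excluded | passes |
| Low exposure, or no epithelial response | not excluded | passes |

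The group that the amendment means to add fails Criterion 3. Those who pass include recent starters, but the documents do not say in what share.

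**2. The plan's own sample size.** "Sample size was calculated to achieve at least 80% power with a significance level of 0.05 using a two-tailed, two-sample t test". The target is "to detect at least 2.0-points mean difference between treatment and placebo groups", with "A sample size of 56 subjects (28 subjects in treatment group and 28 subjects in the placebo group"). No SD is given, so 56 cannot be reproduced independently. Solving backwards for 28 per arm gives a standardised difference of 0.762, so SD = 2.0/0.762 ≈ 2.62. That SD is used below as an assumption.

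**3. Bias and type I error.** Suppose a share f of women in each arm are newly started users and the hormone moves their pain by e points regardless of arm. The expected arm difference is unchanged. A simulation with 28 per arm and no ointment effect gave a mean difference of about 0 and a type I error between 4.9% and 5.1% (f=0.25, e=2 and f=0.50, e=3).

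**4. Added variance.** SD becomes √(2.62² + f(1−f)e²). All f and e are assumed.

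| f | e (NRS points) | SD | Power, 28 per arm | Shift within each arm, f×e |
|---|---|---|---|---|
| 0.10 | 1 | 2.64 | 79.5% | 0.10 |
| 0.25 | 2 | 2.76 | 75.8% | 0.50 |
| 0.50 | 3 | 3.02 | 68.2% | 1.50 |

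**5. Chance imbalance.** With k users among 64 women split 32:32, the number X in one arm is hypergeometric and the arms differ by |2X − k|. The documents do not give k, so a range is shown.

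| k (assumed) | P(differ by 4 or more) | P(differ by 6 or more) |
|---|---|---|
| 4 | 0.113 | 0 |
| 6 | 0.196 | 0.024 |
| 8 | 0.257 | 0.053 |
| 12 | 0.337 | 0.107 |
| 16 | 0.387 | 0.148 |

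By symmetry, the excess falls in the active arm half the time: 0.337/2 ≈ 0.17 for k = 12.

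**6. Size of the resulting shift.** A 4-woman imbalance moves the arm difference by 4/32 = 0.125 of the hormone effect, if every user is a recent starter.

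- Pain, with an assumed effect of 1, 2 or 3 points: 0.125, 0.25 or 0.375. The middle value is 12.5% of the 2.0-point target. The standard error with 32 per arm is 2.62×√(2/32) = 0.655, so 0.25 is 0.38 of a standard error.
- Maturation index, with an assumed effect of 15 or 30 percentage points: 1.9 or 3.75 points.

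**7. Within-arm reading.** Here randomisation gives no protection. With 12 users split 6 and 6, all recent starters and an assumed 30-point effect, each arm's mean index moves by 6/32×30 ≈ 5.6 points with perfect balance and no ointment effect. The amendment itself reports the index in this form, as showing no change on the ointment.

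**The case against.** The strongest reply is that the trial is randomised, double-blind and placebo-controlled. Hormone change independent of arm does not bias the comparison, and chance imbalance is already part of the test's error. This stands. A reader might infer that the primary pain comparison is invalid; the documents do not support that.

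Four other stronger readings also fail:

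- **All hormone exclusions are gone.** They are not. Corticosteroids, anti-androgens and spironolactone stay excluded, as do some of the drugs that item 3's wider clause could have caught.
- **Criterion 3 selects women whose estrogen has not yet acted.** It admits them, along with low-exposure users and non-responders. Since responders are screened out, few users may enter at all.
- **The amendment created the risk of hormone changes during treatment.** The removed items only looked back from entry. None barred a start or stop after randomisation.
- **Hormones will distort the pain result.** The Introduction calls topical estrogen inconsistent or non-efficacious for this pain. An assumed 2-point effect equals the trial's whole target difference, so it is a high assumption.

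It is also fair that drug changes are recorded through week 6, which would support an adjusted or sensitivity analysis. The plan specifies neither.

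**Conclusion.** The concern holds in a limited form. Hormone users may enter with no stability requirement, and their status is collected but not used. The between-arm test stays unbiased on average, with its type I error intact.

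The cost has three parts. Power falls from 80% to between 79.5% and 68.2% across the assumed cases. An imbalance of 4 or more users has a probability of 11% to 39% for 4 to 16 users, which is possible rather than likely. The conclusion of no estrogenic effect cannot be interpreted in users, above all as a within-arm statement.

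The last part matters most, because it is half of the objective and does not depend on imbalance. Any effect on pain is smaller and less certain.

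The missing rule, the unexplained loss of the other-drugs clause and the conflict with Criterion 3 are read directly from the text. The user numbers, hormone effects and SD are assumptions.

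**What to change.** - Add one eligibility sentence: women using estrogen, estrogen-progestin, phyto-estrogen or DHEA enter only if the regimen has been unchanged for the 12 weeks before Visit 1, with no change planned through week 6. The protocol already uses a 12-week look-back, and the three-month drug history lets sites check it.
- Restore the clause on other drugs affecting sexual function, or state why it was dropped.
- Stratify remaining randomisation by hormone use (yes/no), or adjust for it in the analysis.
- Draw the maturation-index and pH conclusion from non-users, compared with placebo, and show users separately.
- Keep women whose regimen changes after randomisation in the analysis, with the change recorded.
- Reconcile the amendment's rationale with Inclusion Criterion 3 and Visit 1 item 15. Until that is done, a stable-use rule would admit few of the women the amendment is meant for.

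The cost is one eligibility sentence, one factor in the IVRS or the model, and one line in the analysis plan. The downsides are that recent starters are excluded and the epithelial conclusion rests on fewer women. Enrolment was also under way when the amendment was written, so stratification can cover only later entrants.
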